#### 4.3.3. Sensitivity Analysis

##### 4.3.3.1. Two-way Tipping Point Analysis

To confirm the robustness of the primary endpoint results, a 2-way tipping point analysis represents varying assumptions for missing data from both treatment groups will be conducted. This sensitivity analysis will focus on missing data at the primary endpoint. Penalty parameters for imputed missing values will be added for both treatment arms. The ANCOVA model for treatment regimen estimand will be conducted after penalty parameters are added. The multiple imputation framework by Rubin (1987) will be used to summarize the results.

The non-inferiority test will be shown by color scale in the figure.

Additionally, imputation under the noninferiority null hypothesis will be conducted by adding 0.4 (NIM) to the imputed data used for treatment regimen estimand (Section [4.3.3](#)) for the LY3209590 group only (Koch 2008). The ANCOVA model for treatment regimen estimand will

be rerun using the adjusted data. The multiple imputation framework by Rubin (1987) will be used to summarize the results.

#### **4.3.3.2. Including Inadvertently Enrolled Participants**

The primary efficacy analysis will be repeated for the mITT population, including participants inadvertently enrolled, for both treatment regimen estimand and efficacy estimand.

#### **4.3.4. Supplementary Analyses**

Additional analysis may be conducted as needed.

### **4.4. Secondary Endpoints Analysis**

#### **4.4.1. Key Secondary Endpoints**

A graphical approach will be used to control the overall type I error for the primary objective and the key secondary objectives. The key secondary objectives will test the superiority of LY3209590 compared with insulin glargine for the following endpoints.

- 1) change in HbA1c from baseline at Week 26 (Visit 23)
- 2) the percentage of participants achieving HbA1c <7% at Week 26 without nocturnal hypoglycemia (<54 mg/dL [3.0 mmol/L] or severe) during treatment phase up to Week 26 (Visit 23), and
- 3) the event rate of nocturnal hypoglycemia (<54 mg/dL or severe) during the treatment phase up to Week 26 (Visit 23).

##### **4.4.1.1. Definition of Endpoint(s)**

See Section 4.3.1 for change in HbA1c from baseline at Week 26 (Visit 23).

The hypoglycemia events will be based on participant entry into an e-diary, which receives all blood glucose (BG) measurements performed by the participant and transmitted via Bluetooth from the study-provided glucometer. The nocturnal period is defined by midnight to 6 AM. The event rate of nocturnal hypoglycemia will be based on the count of the hypoglycemia episodes in the nocturnal period and the corresponding exposure of study intervention.

Participants achieving HbA1c <7% at Week 26 without nocturnal hypoglycemia (<54 mg/dL [3.0 mmol/L], or severe) during treatment phase up to Week 26 will be a composite measure based on HbA1c measured at Week 26 and nocturnal hypoglycemia reported by participants during the 26-week treatment period.

##### **4.4.1.2. Main Analytical Approach**

The superiority test for change in HbA1c from baseline at Week 26 (Visit 23) will be based on the same primary endpoint analysis described in Section 4.3.2.

The percentage of participants achieving HbA1c <7% at Week 26 without nocturnal hypoglycemia (<54 mg/dL [3.0 mmol/L], or severe) during treatment phase up to Week 26 will be analyzed by a composite estimand. This table describes the details.

	Treatment Regimen Estimand	Efficacy Estimand
Analysis population	All participants in Efficacy Analysis Set 1 with non-missing baseline measure.	All participants in Efficacy Analysis Set 2 with non-missing baseline measure
Analysis data	All non-missing observations at Week 26 (Visit 23) during treatment period regardless of the use of study intervention or rescue therapy.	All non-missing observations at Week 26 (Visit 23) during treatment period without discontinuation of study treatment or initiation of rescue therapy.
Endpoint	The composite 
 
binary outcome of HbA1c <7% at Week 26 with 1 indicating achieving HbA1c target
 
binary outcome of no nocturnal hypoglycemia (<54 mg/dL or severe) during 26-week treatment period with 1 indicating no occurrence of nocturnal hypoglycemia.
 
	Same method as for treatment regimen estimand
Missing data handling	
 
For HbA1c, missing values at Week 26 (Visit 23) will be imputed using the same method for the primary endpoint. The binary outcome of HbA1c <7% will be based on the imputed data.
 
For nocturnal hypoglycemia, participant who discontinued the treatment period before Week 26 (Visit 23) is considered as a non-responder (i.e. experiencing the event) and the binary outcome value is 0.
 
	For HbA1c, missing values at Week 26 (Visit 23) will be imputed using multiple imputation with assumption of missing at random. For nocturnal hypoglycemia, participant who discontinued the treatment period before Week 26 (Visit 23) is considered as a non-responder (i.e. experiencing the event) and the binary outcome value is 0.
Analysis model	The composite endpoint will be analyzed using a logistic regression model including treatment, strata (country and routine use of personal CGM or FGM at randomization), baseline HbA1c value, and baseline incidence of nocturnal hypoglycemia. Odds ratio (LY3209590 vs. insulin glargine) and 95% confidence interval, and p-value will be used for treatment comparison. Multiple imputation will be performed, and the statistical inference will be based on the multiple imputation framework by Rubin (1987).	Same model as for treatment regimen estimand

The rate of participant-reported nocturnal hypoglycemia (<54 mg/dL [3.0 mmol/L] or severe) will be analyzed by a negative binomial regression. The analysis details are provided in Section [4.6.2.2.1](#).

#### 4.4.1.3. Sensitivity Analysis

The analyses described in Section [4.4.1.3](#) will be repeated for both the treatment regimen estimand and efficacy estimand by including inadvertent enrolled participants using mITT population.

#### 4.4.2. Supportive Secondary Endpoints

##### 4.4.2.1. Other Efficacy Endpoints

The analyses for CGM variability parameters, insulin dose and patient reported outcomes will be based on the efficacy estimand using EAS2 data.

The analysis of CGM data (except for variability parameters) and fasting glucose from SMBG will be done for both treatment regimen estimand and efficacy estimand. Analysis of covariance for treatment regimen estimand and MMRM model for efficacy estimand similar to those for the primary endpoint with an additional term of baseline HbA1c stratum ( $<8.0\%$ ,  $\geq 8.0\%$ ) will be used.

The variance-covariance structure in the MMRM models for fasting glucose from SMBG and insulin dose will be based on compound symmetry.

For treatment regimen estimand, only subjects with an observation at baseline or at Week 26 (Visit 23) will be included in the analysis. The missing baseline will be imputed using multiple imputation with assumption of missing at random. Missing data at Week 26 (Visit 23) will be imputed as described for the primary HbA1c endpoint.

For the efficacy estimand, only participants with baseline and at least one post baseline observation will be included in the analysis, missing data will be handled by MMRM model.

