#### LY3209590

##### *Initial loading dose*

The initial loading dose aims to optimize and accelerate glycemic control by allowing participants to reach a steady-state concentration faster. The use of a single one-time-only loading dose enables participants to achieve concentrations close to steady state within a few days rather than a period of weeks. This approach minimizes the risk for hyperglycemia during transition to LY3209590 while reaching steady state. In all cases, starting doses will be based upon existing total daily basal insulin doses.

This approach is supported by the Phase 2 Study BDCM and PK model-based simulations.

Details on deriving the loading dose are described in Section [6.5](#).

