##### *Starting weekly dose*

The second dose is the starting weekly dose which is equal to the pre-study total daily basal insulin dose multiplied by 7. The dose will be equivalent to pre-study basal insulin doses, with further adjustment for participants who used insulin glargine U-300 or NPH as their pre-study basal insulin. Details on deriving the starting weekly dose are described in Section [6.5](#).

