### 6.5.2.1. Insulin Glargine General Dosing Information by Visit

At Visit 3 (Week 0), participants will stop their pre-study basal and prandial insulin therapy and initiate study basal and prandial insulin therapy.

The first glargine dose is based on the participant's prior daily basal insulin dose from the week prior to randomization (Visit 3 [Week 0]). If participant's usual basal insulin dosing time overlaps with the visit, they should take the first dose at the site. If participant's usual basal insulin dosing time does not coincide with the visit, they are not required to administer at the site.

This table provides general dosing information across visits for all participants randomized to insulin glargine.

Insulin Glargine General Dosing Information		
Visit	Dose	Additional dosing instruction
Visit 3 (Week 0) starting dose	Equivalent to pre-study usual daily basal insulin dose	Note: If the participant's pre-study basal insulin is glargine U-300 or twice daily NPH, the prior daily basal insulin dose should be reduced by 20% when determining usual daily basal insulin dose.
Visits 4-15 (Weeks 1-12)	Doses will be individualized based on FBG and hypoglycemia events	Dose modifications may occur weekly. Investigators should factor in 4-point SMBG profile and changes to prandial insulin doses as indicated. Dose may be adjusted at any time in response to hypoglycemia.
After Visit 15 (Week 12)	Doses will be individualized based on FBG and hypoglycemia events	
 
• Dose modifications may occur every 4 weeks (Visits 17, 19, and 21) or as clinically indicated. Investigators should factor in 4-point SMBG profile and changes to prandial insulin doses as indicated.
 
• Dose may be adjusted at any time in response to hypoglycemia.
 

Abbreviations: FBG = fasting blood glucose; NPH = neutral protamine Hagedorn; SMBG = self-monitoring blood glucose.

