CGM parameters	The baseline will be derived from the data collected during CGM session prior to the first dose date of study treatment.	The CGM sessions prior to Weeks 4, 12, 26 (Visit 7, 15, 23) in EAS2 for MMRM.  The CGM session prior to Week 26 (Visit 23) in EAS1 for ANCOVA with multiple imputation for missing data.
Basal insulin dose	The baseline period is the screening/lead-in period prior to the initiation of study treatment.  The following variables will be derived: 

• daily dose in U

• weekly dose in U

• dose in U/kg/day

 See detailed derivation of variables in Section 4.4.2.1.	All scheduled visits between Week 0 (Visit 3) and Week 26 (Visit 23) in EAS2 for MMRM.  The following variables will be derived: 

• daily dose in U

• weekly dose in U

• dose in U/kg/day

 See detailed derivation of variables in Section 4.4.2.1.

Analysis	Baseline Observations	Post-Baseline Observations
Prandial (bolus) insulin dose	
The baseline period is the screening/lead-in period prior to the initiation of study treatment.
 
The following variables will be derived:
 
 
• daily dose in U
 
• weekly dose in U
 
• dose in U/kg/day
 
 
See detailed derivation of variables in Section 4.4.2.1.
	
All scheduled visits after Week 0 (Visit 3) and up to Week 26 (Visit 23) in EAS2 for MMRM.
 
The following variables will be derived:
 
 
• daily dose in U
 
• weekly dose in U
 
• dose in U/kg/day
 
 
See detailed derivation of variables in Section 4.4.2.1.

Total insulin dose	
The baseline period is the screening/lead-in period prior to the initiation of study treatment.
 
The following variables will be derived:
 
 
• daily dose in U
 
• weekly dose in U
 
• dose in U/kg/day
 
 
See detailed derivation of variables in Section 4.4.2.1.
	
All scheduled visits after Week 0 (Visit 3) and up to Week 26 (Visit 23) in EAS2 for MMRM.
 
The following variables will be derived:
 
 
• daily dose in U
 
• weekly dose in U
 
• dose in U/kg/day
 
 
See detailed derivation of variables in Section 4.4.2.1.

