#### **4.4.2.1.2. Study Insulin Dose Analysis**

For study basal insulin dose, both average daily and weekly dose during each visit for individual participants will be analyzed. In the LY3209590 group, the average weekly dose of each visit (that is, average of weekly doses since last visit) will be used as the average weekly dose, and the average daily dose will be the average weekly dose divided by 7. For insulin glargine group, the average daily dose since last visit will be computed for each visit, and the average weekly dose will be calculated as average daily dose  $\times$  7. For participants using typical once-daily pre-study basal insulin, the average pre-study basal dose during the screening/lead-in period will be the corresponding baseline daily dose. For participants using pre-study U-300 or Neutral Protamine Hagedorn twice daily (NPH BID), the average pre-study basal dose during the lead-in period multiplying by 0.8 will be the baseline daily dose. The baseline daily dose multiplying by 7 will be the baseline weekly basal insulin dose. The corrected baseline basal insulin dose will be controlled in the model for the insulin dosing analysis.

The daily prandial insulin dose will be calculated as the sum of the prandial insulin doses for morning meal, midday meal, evening meal, and additional dose of the day. All data including 0 dose and single dose of a day are included for analysis. On the first day of study treatment, a participant may have used both pre-study prandial insulin and study provided insulin lispro. Therefore, Week 0 (first day of study treatment) will be excluded from calculating the average daily prandial insulin for baseline and post-baseline period. The weekly prandial insulin dose at each visit is the average daily prandial insulin dose at the same visit  $\times$  7.

The weekly total insulin dose is the sum of average weekly basal insulin dose and average weekly prandial insulin dose. The daily total insulin dose is weekly total insulin dose divided by 7.

The basal/total insulin dose ratio at each visit is the ratio of average weekly basal insulin dose and average weekly total insulin dose at the same visit.

If either weekly basal insulin dose or weekly prandial insulin dose is missing, the total weekly insulin dose and basal/total insulin dose ratio will be set as missing for analysis. Similarly, the total daily insulin dose is also set as missing.

The analysis will be done for

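### Compound symmetry without an empirical SE gives basal dose at Week 26 a visit-averaged SE, which depends on whether and how the one-time loading dose enters the model

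*SAP*

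**What the plan says.** **Covariance.** SAP 4.4.2.1: "The variance-covariance structure in the MMRM models for fasting glucose from SMBG and insulin dose will be based on compound symmetry". No alternative structure or empirical SE is given. The fallback list in SAP 4.3.2 starts from unstructured and belongs to the primary MMRM. The model for CGM targets is referred to that list; the dose model is not.

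**Visits.** For basal dose, the table in SAP 4.1 uses "All scheduled visits between Week 0 (Visit 3) and Week 26 (Visit 23) in EAS2 for MMRM". For prandial dose, total dose and the basal/total ratio, the same table starts after Week 0.

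**Visit value.** For LY3209590, SAP 4.4.2.1.2 says "the average weekly dose of each visit (that is, average of weekly doses since last visit) will be used as the average weekly dose". For prandial insulin only, it adds that "Week 0 (first day of study treatment) will be excluded from calculating the average daily prandial insulin for baseline and post-baseline period". It has no rule for the loading dose.

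**Covariate.** "The corrected baseline basal insulin dose will be controlled in the model for the insulin dosing analysis" (SAP 4.4.2.1.2).

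**Dosing rules.** Protocol 4.3 describes a loading dose given once ("The use of a single one-time-only loading dose enables participants to achieve concentrations close to steady state within a few days"). The table in Protocol 6.5.1.1 sets it at 7 or 21 times the usual daily dose, depending on fasting glucose. Then "The second dose is the starting weekly dose which is equal to the pre-study total daily basal insulin dose multiplied by 7". The first glargine dose is "Equivalent to pre-study usual daily basal insulin dose" (Protocol 6.5.2.1). Both arms are then titrated individually.

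**The concern.** Homogeneous compound symmetry gives every visit the same variance. Its SE for the Week 26 contrast therefore comes from the average of the visit variances, not from the variance at Week 26.

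The protocol's rules make that average a poor guide for basal dose. Two of the starting doses are almost fixed by the covariate. The loading dose is not, because participants with the same baseline differ threefold according to fasting glucose. Doses then spread with titration.

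The SAP also leaves open how the loading dose reaches the model. The 4.1 table includes Week 0, so the dose could be the Visit 3 value. Averaging since the last visit could place it at Visit 4, alone or averaged with the first weekly dose. A programmer could also drop it, by analogy with the prandial rule. Each choice gives a different SE from identical Week 26 data.

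At stake are the CI and p-value for basal insulin dose at Week 26, a named other-secondary endpoint. SAP 4.1 plans 95% CIs and p-values for comparisons of this kind.

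**Working it through.** **No figure to reproduce.** The documents give no SD, SE or power for insulin dose. As a check on n, 284 per arm with SD 1.1 and difference 0.3 gives 90.1% power for HbA1c (SAP 5 states 90%).

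**Inputs from the documents.** Visits 3 to 23 are 21 visits. There are 284 completers per arm (670 × 0.85 / 2 = 284.75). Dose rules are those of Protocol 6.5.1 and 6.5.2.

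**Assumed inputs (base case).** Pre-study dose 40 U/day (SD 25), that is 280 (SD 175) U/week; 70% with lead-in fasting glucose above 120 mg/dL; spread of dose need 0.25 on the log scale. Simulating the dose rules gave these residual SDs given baseline, both arms pooled, in U/week: loading visit 268, Visit 4 24, Week 12 76, Week 26 84.

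**Loading-visit SD by hand.** Let B be the weekly baseline dose. The loading dose is B(1 + 2Z), where Z = 1 with probability 0.7.
- Variance from Z: 4 × 0.7 × 0.3 × E(B²) = 0.84 × (280² + 175²) = 0.84 × 109,025 = 91,581.
- Misfit of the common baseline slope (about 1.1 in the runs, against 1 + 2 × 0.7 = 2.4 at this visit): 1.3² × 175² = 51,756.
- Total in LY3209590: 143,337. Glargine contributes about zero, so the pooled SD is √(143,337 / 2) = 268.

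**Week 26 SE.** SE ≈ √(variance × 2/284) = SD × 0.0839. Using Week 26's own variance, 84 × 0.0839 = 7.05. The SD of the estimate over 400 simulated trials was 7.3.

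**Compound symmetry SE.** Replace the Week 26 variance by the mean over visits. With the loading dose left out, the simulated SE is 5.66. The mean variance is then (5.66 / 0.0839)² ≈ 4,549, or 90,981 summed over 20 visits. From there:
- Whole, at Visit 3: (90,981 + 268²) / 21 = 7,753, SE 7.39.
- Whole, at Visit 4: (90,981 − 24² + 268²) / 20 = 8,111, SE 7.56.
- Averaged with the Visit 4 dose: this value is B(1 + Z). Its variance in LY3209590 is 0.21 × 109,025 + (1.7 − 1.1)² × 175² = 33,920. Pooled with glargine it is 33,920 / 2 + 24² = 17,536. Then (90,981 − 576 + 17,536) / 20 = 5,397, SE 6.17.

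| Loading dose | SE by hand | SE simulated | Against 7.05 | Simulated coverage |
|---|---|---|---|---|
| Whole, Visit 3 | 7.39 | 7.42 | +5% | 94.3% |
| Whole, Visit 4 | 7.56 | 7.59 | +8% | 94.5% |
| Averaged into Visit 4 | 6.17 | 6.17 | −12% | 91.5% |
| Left out | taken as start | 5.66 | −20% | 88.5% |

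Coverage rests on 400 trials, so its Monte Carlo error is about 1 to 1.6 points. Moving the whole loading dose artificially to Visit 12 gave 7.42, the same as at Visit 3.

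**With dropout.** With 335 per arm and 15% dropout, the compound symmetry SE was 7.15 (Visit 3), 7.33 (Visit 4), 5.73 (averaged) and 5.13 (left out). The sandwich SE was 6.62 to 6.66 throughout.

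**Range over assumption sets.** Ratio of the compound symmetry SE to the correct one, with coverage = 2Φ(1.96 × ratio) − 1:
- left out: 0.75 to 0.86, coverage 85.8% to 90.8%;
- averaged into Visit 4: 0.77 to 1.01, coverage 86.9% to 95.2%;
- whole in one visit: 0.81 to 1.43, coverage 88.8% to 99.5%.

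**The case against.** **A simple structure is defensible.** An unstructured matrix for 21 visits has 21 × 22 / 2 = 231 parameters, so a parsimonious choice is reasonable. This stands. It supports compound symmetry as a working structure, not reliance on its model-based SE.

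**Homogeneous is an inference.** SAP 4.3.2 lists the heterogeneous and homogeneous forms as separate items, so the unqualified term most naturally means the latter. If the heterogeneous form was meant, large-sample coverage in the simulated scenarios was 93.7-94.7% and the problem largely disappears. One added word would settle it.

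**Real early doses vary more than the rules imply.** The covariate is a diary average, the investigator sets the dose, and SAP Appendix 2 plans to count departures from the algorithm. In one base case with Week 0 included, such variation raised coverage from 91.2% to 92.3% (20% variation) and 93.7% (30%). It reduces the effect there but does not remove it.

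**A reader might infer that the CI is generally too narrow.** The documents give no dose variances, and the sign depends on them. With the loading dose whole at Week 0 and a mean log increase in need of 0.1, coverage was 99.2, 97.7, 94.3, 91.6 and 89.8% at log SDs of 0.15, 0.2, 0.3, 0.4 and 0.5. Only leaving the dose out gave too small an SE in every set tried, and that reading goes against the 4.1 table.

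**A reader might infer that it matters which visit holds the loading dose.** It hardly does. Compound symmetry treats visits as exchangeable, and 7.42 against 7.59 reflects 21 rather than 20 visits. What matters is whether the dose enters, and whether whole or averaged.

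**The consequence is small.** This stands: the endpoint is outside the alpha-controlled family, and the estimate is nearly that of a Week 26 ANCOVA.

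**Conclusion.** The point holds as a minor one. The stated method gives basal dose at Week 26 an SE built from other visits' variances, and the SAP leaves open a choice that moves that SE. Unequal variances follow from the protocol's own rules together with the baseline covariate. The size rests on assumed dose distributions, so the ranges above are illustrations and carry no overall direction.

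The point estimate, the primary and key secondary tests and the stated power are unaffected. No figure is claimed for bolus dose, total dose or the basal/total ratio. It would be tempting to extend the point to SMBG fasting glucose, which shares the sentence in 4.4.2.1. The dosing argument does not carry over, and a Week 26 ANCOVA is also planned for that endpoint.

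**What to change.** In SAP 4.4.2.1, for the basal-dose MMRM, keep compound symmetry as the working structure. Base the SE, CI and p-value on the empirical (sandwich) estimator, and name a degrees-of-freedom method that works with it. The section names none for this model. The Kenward-Roger method of 4.3.2 is model-based and would not protect against a wrong variance structure. Heterogeneous compound symmetry, or unstructured if it converges, is also acceptable.

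In SAP 4.4.2.1.2, state how the loading dose enters the visit-level basal dose: whole and at which visit, averaged with the Visit 4 dose, or left out. Leaving it out without changing the SE method would make the SE smaller still.

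In simulated trials with 335 per arm and 15% random dropout, sandwich coverage was 94.0-96.0% in all 12 combinations of scenario and visit handling.

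The cost is a few lines of SAP text, one program option and a different degrees-of-freedom method. The CI may become somewhat wider or narrower. In one base case with Week 0 in the model, the half-width goes from 1.96 × 1.38 = 2.7 to 1.96 × 1.60 = 3.1 U/day. The sandwich SE does not correct bias from dose-related dropout.

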Basal/total insulin dose ratio	
The baseline period is the screening/lead-in period prior to the initiation of study treatment.
 
See detailed derivation of variables in Section 4.4.2.1.
	
All scheduled visits after Week 0 (Visit 3) and up to Week 26 (Visit 23) in EAS2 for MMRM.
 
See detailed derivation of variables in Section 4.4.2.1.

Fasting glucose by SMBG	
The baseline period is the lead-in period up to the day of first dose of study treatment. Baseline will be derived as the average of all fasting glucose measurements between V2 date and the first dose date.
	
All available data after the day of first dose of study treatment up to Week 26 (Visit 23) in EAS2 for MMRM.
 
Values at each visit will be derived as average of all fasting glucose measurements from the day post prior visit up to the day of the next visit.
 
Data at Week 26 (Visit 23) in EAS1 for ANCOVA with multiple imputation for missing data.

Analysis	Baseline Observations	Post-Baseline Observations
Fasting serum glucose	The baseline is the last non-missing assessment prior to or on the day of the first dose of study treatment.	
All scheduled visits after the day of first dose up to Week 26 (Visit 23) for MMRM
 
Planned measurements at scheduled visits will be included.
 
Data at Week 26 (Visit 23) in EAS1 for ANCOVA with multiple imputation for missing data.

Participant-reported hypoglycemia	The baseline period is the screening/lead-in period prior to the day of first dose of study treatment.	
 
• Treatment period starts on the day of first dose of study treatment and ends 
 
◦ at Week 26 (Visit 23) if completed treatment and Visit 23
 
◦ on the last dose date of study treatment + 10 days for LY3209590, +1 day for glargine if discontinued study treatment early
 
 
 
• Post-treatment period starts from 
 
◦ Week 26 (Visit 23)+1 day if completed treatment and Visit 23
 
◦ last dose date of treatment +11 days for LY3209590, +2 days for glargine if discontinued study treatment early
 
 
 
 
and ends on the last date in the study

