#### 4.3.2. Main Analytical Approach

The primary objective is to test the hypothesis that LY3209590 is noninferior to insulin glargine on glycemic control in the targeted study population. The noninferiority test will be based on the

- *treatment regimen estimand* for the US FDA submission, and
- *efficacy estimand* for registrations in other countries.

The full significance level of 0.05 will be used for each estimand.

This table provides the details of treatment regimen estimand and efficacy estimand.

	Treatment Regimen Estimand	Efficacy Estimand
Analysis Population	All participants in EAS1 with non-missing baseline measure	All participants in EAS2 with non-missing baseline measure and at least 1 non-missing post-baseline scheduled measure
Analysis Data	All non-missing observations at baseline and Week 26 (Visit 23) regardless of the use of study intervention or rescue therapy.	All non-missing observations at baseline and all scheduled post-baseline timepoints during treatment period (that is, Weeks 2, 4, 12, 16, and 26) prior to the date of last study dose + 10 days for LY3209590 (+1 day for glargine), or the initiation of rescue therapy, whichever is earlier for participants who had intercurrent events

	Treatment Regimen Estimand	Efficacy Estimand
Missing Data	
There may be missing values at Week 26 (Visit 23) due to early study discontinuation. The missing values will be imputed using multiple imputation by the retrieved dropout approach. The retrieved dropout participants are those who discontinue study intervention prior to Week 26 but have non-missing measures at Week 26 in the same treatment arm. If there are only a limited number of retrieved participants that leads to a failure in performing the multiple imputation analysis, such as the model cannot converge, or the number of retrieved dropout participants is small (i.e., at least 1 arm has < 8 participants who discontinued study treatment early and have endpoint visit measurements), the missing HbA1c at Week 26 will be imputed by return-to-baseline multiple imputations approach (Qu and Dai, 2022).
	
The MMRM model will be used, and the missing values will be handled in the MMRM analysis under the assumption of missing at random.

	Treatment Regimen Estimand	Efficacy Estimand

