### Minimum Data Available to Define a Valid Period of the Day and CGM Session

Period	Definition	Minimum Valid CGM Time Period for a Session
Valid CGM Day (00:00-23:59)	$\geq 70\%$ of expected values available ( $\geq 202$ of 288 values)	3 valid CGM days define a CGM session for 24-hour

Valid CGM Nighttime (00:00-05:59)	$\geq 70\%$ of expected values available ( $\geq 50$ of 72 values)	3 valid CGM days define a CGM session for Nighttime
Valid CGM Daytime (06:00-23:59)	$\geq 70\%$ of expected values available (151 of 216 values)	3 valid CGM days define a CGM session for Daytime

Sensitivity analysis will be done for selected parameters including all CGM data.

The ambulatory glucose profile during the 24-hour period will be generated with interquartile ranges, at treatment-group level by CGM session, based upon the observed and imputed CGM measures.

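### SAP 4.4.2.1 drops participants without a baseline from the efficacy-estimand models for CGM and SMBG fasting glucose, although it imputes that baseline for the treatment regimen estimand; the cost is a little precision

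*SAP*

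**What the plan says.** SAP 4.4.2.1 (Other Efficacy Endpoints) first divides the endpoints by estimand. Two families get both: "The analysis of CGM data (except for variability parameters) and fasting glucose from SMBG will be done for both treatment regimen estimand and efficacy estimand". The others get one: "The analyses for CGM variability parameters, insulin dose and patient reported outcomes will be based on the efficacy estimand using EAS2 data".

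It then sets the inclusion rules.

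- **Treatment regimen estimand (ANCOVA, EAS1):** "only subjects with an observation at baseline or at Week 26 (Visit 23) will be included in the analysis". For those without a baseline, "The missing baseline will be imputed using multiple imputation with assumption of missing at random".
- **Efficacy estimand (MMRM, EAS2):** "For the efficacy estimand, only participants with baseline and at least one post baseline observation will be included in the analysis". The sentence ends by leaving missing data to the MMRM.

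The primary HbA1c MMRM in SAP 4.3.2 has the same requirement: "All participants in EAS2 with non-missing baseline measure and at least 1 non-missing post-baseline scheduled measure".

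The baselines differ in how easily they go missing. For SMBG fasting glucose (SAP 4.1), "Baseline will be derived as the average of all fasting glucose measurements between V2 date and the first dose date". For CGM, SAP 4.1 takes the session before the first dose, and SAP 6.6 requires a minimum amount of data: "3 valid CGM days define a CGM session for 24-hour", each valid day having at least 70% of expected readings (202 of 288).

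**The concern.** The efficacy-estimand rule discards observed on-treatment data. A participant whose lead-in CGM session yields two valid days, but whose later sessions are complete to Week 26, is left out of the efficacy-estimand model for time in range. The MMRM's handling of missing data does not help, because it applies to the repeated response and not to a missing covariate. For the same parameter, the same section keeps that participant in the treatment regimen analysis by imputing the baseline. No reason is given for the difference, and it has nothing to do with discontinuation or rescue, the intercurrent events that separate the two estimands.

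At stake are confidence intervals somewhat wider than the data allow for four listed other secondary endpoints: time in range, time below 54 mg/dL, time above 180 mg/dL and fasting SMBG.

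**Working it through.** **Plan's own figures.** The SAP states no power or precision for CGM, SMBG or insulin dose. Its HbA1c figures reproduce. With 284 per arm and SD 1.1, SE = 1.1 × √(2/284) = 0.0923. Power at 0.3 is Φ(0.3/0.0923 − 1.96) = 90.1% (stated: 90%). Power at 0.4 is 99.1% (stated: above 99%). These do not depend on the rule examined here.

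**Inputs for the precision check**

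- *m*, the fraction without a baseline: not in the documents; assumed 1% to 10%.
- *ρ*, the correlation of baseline with the Week 26 value: not in the documents; assumed 0.3 to 0.7.
- About 670 randomized (SAP 5), used only to turn *m* into a count.

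**Formula.** Adjusting for baseline reduces the outcome variance from σ² to σ²(1 − ρ²). A participant kept without an observed baseline therefore carries about (1 − ρ²) of the information of one who has it. Per participant randomized:

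- dropped: information ∝ (1 − m)
- kept: information ∝ (1 − m) + m(1 − ρ²)

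CI width, dropped relative to kept = √{[(1 − m) + m(1 − ρ²)] / (1 − m)}

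Example, m = 0.10 and ρ = 0.5: √[(0.90 + 0.10 × 0.75)/0.90] = √1.0833 = 1.041.

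| m | about, of 670 | ρ = 0.3 | ρ = 0.5 | ρ = 0.7 |
|---|---|---|---|---|
| 1% | 7 | +0.5% | +0.4% | +0.3% |
| 2% | 13 | +0.9% | +0.8% | +0.5% |
| 5% | 34 | +2.4% | +2.0% | +1.3% |
| 10% | 67 | +4.9% | +4.1% | +2.8% |

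The approximation treats Week 26 as observed for the participants kept.

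**Where a baseline is likely to be missing**

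- *SMBG fasting glucose.* Any single lead-in reading gives a baseline. Protocol 4.1 asks for at least 3 fasting readings a week from Visit 2, and Protocol 6.5.1.1 uses the three most recent to set the LY3209590 loading dose. Missing values should be rare.
- *CGM.* There is one lead-in session, with Visit 3 falling 11 to 17 days after Visit 2 (Protocol 1.3), and no fallback if it yields fewer than 3 valid days. Protocol 8.1.1.2 foresees sessions under its 80% compliance threshold. This is the likeliest place for a loss, though no document gives a rate.

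**Bias.** These baselines come from data up to first dose, essentially before treatment. Excluding on them should not tilt the comparison between arms.

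**The case against.** The strongest defence is consistency: the primary HbA1c MMRM uses the same rule, and SAP 4.4.2.1 says the secondary models resemble the primary ones. That explains the wording but does not carry over to CGM. HbA1c has a safety net, since a central-laboratory screening value is an entry criterion (Protocol 5.1) and baseline is the last non-missing value up to first dose (SAP 4.1). The rule therefore costs almost nothing for HbA1c.

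A second defence is that the SAP already plans a sensitivity analysis on all CGM data (SAP 6.6) and summaries of missing-data patterns (SAP 4.4.2.1.1). The first covers only selected parameters and cannot supply a baseline where none was recorded. The second describes the problem without restoring anyone.

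Three limits on the point do stand.

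- A reader might infer that the SAP is also inconsistent for CGM variability and insulin dose. It is not. Those endpoints have no treatment regimen analysis, so no baseline is imputed for them anywhere. Their first-dose rules also require the prior daily basal dose (Protocol 6.5.1.1 and 6.5.2.1), so a missing basal baseline is unlikely.
- A reader might infer that harmonizing the rule would put both estimands on the same people, or that a gap between them reflects who was dropped. Neither follows. The treatment regimen analysis also keeps participants with only a baseline, and it uses Week 26 in EAS1 where the MMRM uses all sessions or visits in EAS2. If a missing baseline is unrelated to arm, dropping those participants should add only chance variation to the gap.
- A reader might assume a double-digit missing rate across all these endpoints. Nothing in the documents supports one, and for SMBG the collection rules point the other way.

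**Conclusion.** The point holds as a minor one. For CGM parameters other than variability and for SMBG fasting glucose, the efficacy-estimand MMRM discards usable on-treatment data that the same section retains for the other estimand, without a stated reason. The cost is precision, mainly for CGM: an interval under 1% wider at 2% missing and about 3 to 5% wider at 10% missing. Both rates, and the correlation range of 0.3 to 0.7, are assumptions. There is no reason to expect between-arm bias from the baseline requirement. These endpoints lie outside the multiplicity scheme, so no primary or key secondary conclusion depends on it.

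**What to change.** In SAP 4.4.2.1, replace the efficacy-estimand inclusion rule for CGM parameters (other than variability) and SMBG fasting glucose with wording to this effect: *All EAS2 participants who have one or more post-baseline observations enter the model. A missing baseline is multiply imputed under missing at random, with an imputation model that uses the post-baseline sessions or visits. Alternatively, baseline is modelled as a response with a mean common to both arms.* The SAP should name one of the two.

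The same handling can be extended to CGM variability and insulin dose as an optional gain in precision, not as the repair of an inconsistency.

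If the sponsor keeps the current rule, it should give the reason and report, by arm and endpoint, how many participants are excluded for lack of a baseline.

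The cost is modest extra programming. The imputation planned for the treatment regimen ANCOVA targets Week 26 in EAS1, so it cannot simply be reused; the MMRM needs a longitudinal imputation step. No new data are needed, and the primary and multiplicity-controlled endpoints do not change.
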